#### 7.2.4 Periorbital Aesthetic Appearance Questionnaire

- Subject's assessment of periorbital area as measured by the PAAQ ([Appendix 9](#))

## 8 Discontinuation Criteria

### 8.1 Early Discontinuation of the Study

An investigator may stop the study at his/her study site at any time. The Sponsor may discontinue the study (and/or participation of a single study site) for any reason with appropriate notification. If conditions arise during the study that indicate that the study or an investigational site should be terminated, the Sponsor, the investigator, the study monitor, REB, and/or regulatory agencies will take appropriate action after consultation. Conditions that may warrant termination of the study or investigational site include, but are not limited to:

- Discovery of an unexpected, serious, or unacceptable risk to subjects enrolled in the study
- The decision on the part of the Sponsor to suspend or discontinue testing or evaluation of the study treatment
- Failure of an investigator to comply with pertinent national or state regulations, REB-imposed conditions, or protocol requirements
- Submission of knowingly false information to the Sponsor, study monitor, the REB, or any regulatory agency by the investigator

If the study is prematurely terminated or suspended due to safety issues, the Sponsor will inform all investigators and applicable regulatory authorities of the termination or suspension and the reason(s) for the termination or suspension. The REB is also to be informed promptly and provided the reason(s) for the termination or suspension by the Sponsor or by the investigator, as specified by the applicable regulatory requirements. If a premature termination or suspension occurs, the Sponsor shall remain responsible for providing resources to fulfill the protocol obligations and existing agreements for follow-up of subjects enrolled in the study, and each investigator or authorized designee will promptly inform enrolled subjects, if applicable.

### 8.2 Early Discontinuation of Individual Subjects

A subject may voluntarily withdraw from the study at any time. Notification of early subject discontinuation from the study and the reason for discontinuation will be made to the sponsor and will be clearly documented on the appropriate eCRF. In the event of subject discontinuation, every effort should be made to have the subject complete the primary endpoint FACE-Q Satisfaction with Facial Appearance Overall questionnaire.

It is the right and responsibility of the investigator to discontinue a subject's participation when the subject's health or well-being is threatened by continuation in the study. In the event of premature discontinuation, the investigator should determine the primary reason for discontinuation.

A subject who is withdrawn from the study prior to initiation of treatment may be replaced. Discontinued subjects will not be replaced.

The following are circumstances that could result in a subject's discontinuation from the study:

- AEs or SAEs that render the subject unable to continue study participation
- Protocol violation
- Subject voluntarily withdraws consent
- Non-compliance with study requirements
- Discretion of investigator (must document reason on eCRF)
- Progressive injury (at the discretion of the investigator)
- Changes in the subject's condition that render the subject unacceptable for further participation, in the judgment of the investigator
- Pregnancy (required discontinuation)
- Lost to follow-up
- Unable to physically or mentally tolerate the use of the test treatment
- Exclusion criterion met

## 9 Treatments

The study treatments are:

- **BOTOX:** The dose and the number of injection points may be adapted to the needs of the subject, based on their characteristics and location of the muscles to be treated. Subjects will receive at least one BOTOX treatment in the following areas: GLs, CFLs, and FHLs.)
- **HArmonyCa Lidocaine:** The investigator will determine the appropriate volume to be injected during initial and touch-up treatments based on his/her clinical experience. The maximum total volume of HArmonyCa Lidocaine allowed per subject for the initial and touch-up treatment combined is 4 syringes (5 mL).
- **JUVÉDERM:** The investigator will determine the appropriate volume to be injected during initial and touch-up treatments based on his/her clinical experience
  - JUVÉDERM VOLITE [REDACTED]: The maximum total volume of JUVÉDERM VOLITE [REDACTED] allowed per subject for the initial and touch-up treatments combined is 4 syringes (4 mL).
  - JUVÉDERM VOLBELLA with Lidocaine: The maximum combined total volume allowed per subject for all facial areas treated for both the initial and touch-up treatments combined is 2 syringes (2 mL).
  - JUVÉDERM VOLIFT with Lidocaine: The maximum total volume of JUVÉDERM VOLIFT with Lidocaine allowed per subject for the initial and touch-up treatments combined is 4 syringes (4 mL).
  - JUVÉDERM VOLUMA with Lidocaine: The maximum total volume of JUVÉDERM VOLUMA with Lidocaine allowed per subject for the initial and touch-up treatments combined is 4 syringes (4 mL).
  - JUVÉDERM VOLUX with Lidocaine: The maximum total volume of JUVÉDERM VOLUX with Lidocaine allowed per subject for the initial and touch-up treatments combined is 4 syringes (4 mL).

The investigator should not inject greater than 20 mL of filler (Juvéderm and HArmonyCa) per 60 kg (130 lbs.) body mass per year for a single subject.

The chemical compositions for each of the study products intended for subject treatment are provided in [Appendix 8](#).

All study drugs/devices must be stored in a secure area, accessible only to study personnel. The sponsor will provide each study site with sufficient study treatments (study drugs and devices) for all study subjects, including back-up study treatments.

The sponsor will provide the most recent country-specific Directions for Use and Product Monographs for each product to each investigator to be used in study treatment. Details of formulation, storage, and handling, and complete instructions for administration of treatments can be found in the respective product information for each study drug/device.

All unused study treatments should be retained for return to the sponsor.

All products will be used as per their license only. Further details on the products can also be found in the currently approved Directions for Use and Product Monographs.

### **9.1      Rescue Medications**

No product licensed in Brazil is approved as a rescue medication. Administration of hyaluronidase is considered to be “off-label” and it has not been provided as a part of the study regimen. It should only be used if in the investigator’s judgment it is deemed to be necessary to inject hyaluronidase for the safety of the subject, in that situation, the investigator may inject at his/her discretion as a concomitant medication, capturing relevant information.

### **9.2      Treatment Compliance**

The investigator is responsible for compliance with the protocol at the investigational site. The investigator is also responsible for reporting all issues of protocol non-compliance to the respective REB and to the sponsor. A representative of the sponsor will make frequent contact with the investigator and his/her research staff and will conduct regular monitoring visits at the site to review subject and study drug and device accountability records for compliance with the protocol, e.g., subject eligibility criteria, volume of product injected, procedures performed, and follow-up visit schedule.

## 10 Adverse Events

Throughout the course of the study (from the date of informed consent), all AEs will be monitored and recorded on the AE eCRF. If an AE occurs, the first concern will be the safety of the study participant. All AEs related to study treatments or procedures will be followed until resolved or stabilized or until follow-up is no longer possible.

### 10.1 Drug Adverse Events

An AE from a drug is defined as any undesired medical occurrence in a subject receiving a pharmaceutical product and which does not necessarily have a causal relationship with this treatment. An AE can therefore be any unfavorable sign and unintended sign (including an abnormal laboratory finding), symptom, or disease temporally associated with the use of a medicinal (investigational) product, whether or not related to the medicinal (investigational) product.

Adverse events will be assessed and documented, as appropriate, throughout the study (i.e., after informed consent has been obtained). At each visit, the investigator will begin by querying for AEs by asking each subject a general, non-directed question such as "How have you been feeling since the last visit?" Directed questioning and examination will then be done as appropriate. All reported AEs will be documented on the AE eCRF.

### 10.2 Medical Device Adverse Events

An AE from a medical device is defined as any undesirable physical, psychological or behavioral effect experienced by a subject during his/her participation in a study, in conjunction with the use of the device, whether or not considered related to the procedure or the product. Adverse events may include, but are not limited to, subjective or objective symptoms spontaneously offered by the subject, solicited via subject interviews, uncovered by review of concomitant medications, therapies, and treatments, and/or observed by the investigator. The investigator will record the description (sign, symptom and diagnosis), location, onset, resolution, seriousness, severity, cause, and action taken for any event on the AE eCRF.

Disease signs and symptoms that existed prior to the study injections are not considered AEs unless the condition recurs after the subject has recovered from the pre-existing condition or the condition worsens in intensity or frequency during the study.

### 10.3 Injection Site Reactions

Injection site reactions following treatment with dermal fillers include redness, pain after injection, tenderness to touch, firmness, swelling, lumps/bumps, bruising, itching, and discoloration. Subjects will maintain a diary record of the presence, location, frequency, severity, and duration of any ISR for 30 days after each filler treatment.

Subjects will indicate the occurrence of an ISR and severity (none, mild, moderate, severe) of the event. NOTE: ISRs that persist longer than 30 days should be recorded and followed to resolution on the AE eCRF. If an ISR is ongoing or appears after the subject's last study visit, it will be followed up by the sponsor Product Surveillance separate from this study protocol.

## 10.4 Unusual Failure in Efficacy

Unusual Failure in Efficacy is defined as failure of a health product to produce the expected/intended effect, which may result in an adverse outcome for the patient, including an exacerbation of the condition for which the health product is being used. One example of unusual failure in efficacy is a previously well-stabilized condition that deteriorates when the patient changes to a different brand or receives a new prescription. Another example of a case that should be reported on an expedited basis is a life-threatening infection where the failure in efficacy seems to be due to the development of a newly resistant strain of bacterium previously regarded as susceptible.

Any unusual failure in efficacy reported during the conduct of the study should be immediately reported to a sponsor representative and recorded in the appropriate eCRFs.

The Investigator must:

1. Notify the sponsor immediately. For Emergency Phone Numbers see front of protocol. Fax completed Unusual Failure in Efficacy reporting form to: [name].
2. Obtain and maintain in his/her files all pertinent medical records, information, and medical judgments from colleagues who assisted in the treatment and follow-up of the subject.

## 10.5 Serious Adverse Events

### 10.5.1 Serious Adverse Events Definition

An SAE is any AE that either led to death; resulted in a life-threatening illness or injury; resulted in a permanent impairment of a body structure or a body function; required in-patient hospitalization or prolongation of existing hospitalization; resulted in medical or surgical intervention to prevent permanent impairment to body structure or a body function; led to fetal distress, fetal death or a congenital abnormality or birth defect.

Pre-planned surgeries or procedures for pre-existing, known medical conditions for which a subject requires hospitalization are not reportable as an SAE. Any pre-planned surgery or procedure should be clearly documented in the site source documents by the investigator at the time of the subject's entry into the study.

NOTE: the sponsor considers all cancer AEs as SAEs. Pregnancy by itself is not generally considered an AE.

### 10.5.2 Serious Adverse Event Reporting Requirements

Any SAE occurring during the study period (beginning with informed consent) and through 30 days after study exit must be reported within 24 hours to the sponsor on 2 SAE forms. The drug, and device SAE forms must be recorded and e-mailed per this protocol section. All subjects with an SAE must be followed up and the outcomes reported.

The principal investigator must supply the sponsor and the REB with any additional requested information (e.g., hospital discharge summary, autopsy reports and terminal medical reports) only upon request. The sponsor will evaluate all SAEs for both drug and device. Device SAEs will be documented in writing as to whether they meet the definition of an USADE. These will be reported to all participating investigators, the regulatory authorities, and the REB.

In the event of an SAE, the investigator must:

1. Notify the sponsor immediately (within 24 hours) using the SAE reporting forms. Emergency phone numbers and relevant sponsor personnel contacts are below.

Obtain and maintain in his/her files all pertinent medical records, information, and medical judgments from colleagues who assisted in the treatment and follow-up of the subject.

Provide the sponsor with a complete, written case history (AE report form), including copies of supporting reports (e.g., progress notes, laboratory reports), upon request and a statement from the investigator as to whether the event was or was not related to the use of the investigational drug or device.

Promptly inform the governing REB of the SAE, if it is device-related, as required by the REB, local regulations, and the governing health authorities.

### **10.6 Unanticipated Serious Adverse Device Effects**

An unanticipated serious adverse device effect (USADE) is any device-related SAE that meets one or more of the following criteria:

- Is not identified in nature, severity, or frequency in current literature on the product
- Is life-threatening, even if temporary in nature
- Results in permanent impairment of a body function or permanent damage to a body structure

- Necessitates medical or surgical intervention to preclude permanent impairment of a body function or permanent damage to a body structure

Also considered an USADE is any device malfunction that would be likely to cause or contribute to a death or serious injury if the malfunction were to recur. The investigator will notify the sponsor within 24 hours of any device malfunction and a representative will provide instruction for the return of any faulty syringe for evaluation.

## 10.7 Assessment of Adverse Events

### 10.7.1 Severity

Assessment of severity of an AE will be rated according to the definitions in [Table 10.1](#) and the worst grade documented. The investigator will review these [definitions](#) with the subject for use when completing the subject diary. For events reported on the AE eCRF, e.g., ISRs that persist beyond the diary period and other AEs, the investigator will determine the severity classification based on these definitions, his/her experience in the use of dermal fillers and/or the subject's description of the event.

The term “severe” is used to describe the intensity of an AE; the event itself could be of relatively minor clinical significance (e.g., “severe headache”). This is not the same as “serious.” Seriousness of AEs is based on the outcome of an AE and usually associated with events that pose a threat to a subject’s life or functioning.

**Table 10.1 Classification of Adverse Events by Intensity**

Grade 1 (Mild)	The symptom is barely noticeable to the study subject and does not influence performance or functioning. Concomitant medication is not ordinarily indicated for relief of mild AEs.
Grade 2 (Moderate)	The symptom is of sufficient severity to make the study subject uncomfortable and to influence performance of daily activities. Concomitant medication may be indicated for relief of moderate AEs.
Grade 3 (Severe)	The symptom causes severe discomfort, sometimes of such severity that the study subject cannot continue in the study. Daily activities are significantly impaired or prevented by the symptom. Concomitant medication may be indicated for relief of severe AEs.
Not applicable	In some cases, an AE/ISR may be an “all-or-nothing” finding that cannot be graded.

Abbreviations: AE = adverse event, ISR = injection site reaction.

## 10.7.2 Relationship to Study Product

A determination will be made, by the investigator, of the relationship, if any, between an AE and any study product, anesthesia employed, the study device, or the injection procedure, as applicable, using the guidelines presented in **Table 10.2**.

**Table 10.2 Guidelines for Determining the Relationship Between Adverse Event and the Study Product**

Highly Probable	This causal relationship is assigned if the AE starts a reasonable time after the administration of study product, stops/improves when the study product is stopped, and could reasonably be explained by known characteristics of the study product.
Probable	This causal relationship is assigned when the AE starts a reasonable time after the administration of study product, stops/improves when the study product is stopped, and could not be reasonably explained by known characteristics of the subject's clinical state.
Possible	This causal relationship is assigned when the AE starts a reasonable time after the administration of study product but could be produced by the subject's clinical state or other modes of therapy administered to the subject.
Not Related	This causal relationship is assigned when the time association or the subject's clinical state is such that the study product was not likely to have had an association with the observed AE.

Abbreviations: AE = adverse event.

### 10.7.3 Adverse Event Follow-up

All AEs (including SAEs) must be recorded on the appropriate eCRF. All AEs that are treatment-related and unexpected (not listed as treatment-related in the current package insert or directions for use) must be reported to the governing REB as required by the REB, local regulations, and the governing health authorities. Any AE that is marked “ongoing” at the exit visit must be followed up as appropriate.

### 10.8 Exposure to Investigational Product during Pregnancy

Marketing Authorization Holders (MAHs) are expected to follow up all pregnancy reports from health professionals and consumers where the embryo/fetus could have been exposed to one of its health products. For consumer reports, it is appropriate to seek permission to only follow up with the health professional. The MAH must apply all principles outlined in this guidance document and the regulations pertaining to reporting requirements, including determination of seriousness and minimal criteria for submitting an adverse reaction (AR) report. Reports of pregnancy exposure with no associated ARs should not be reported as ARs. When an active substance, or one of its metabolites, has a long half-life, this should be taken into account when considering whether a fetus could have been exposed (e.g., if health products taken before the gestational period should be considered).

Pregnancy by itself is not generally considered an AE. The occurrence of an adverse pregnancy outcome may constitute an AE or an SAE, making the collection of pregnancy-related data and pregnancy outcomes valuable. Inpatient hospitalization for a normal vaginal delivery or elective abortion of a normal fetus does not constitute a SAE. If no serious injury occurred to the mother or fetus, then there is no reason to qualify pregnancy in the setting of hospitalization as a SAE. Accidental, therapeutic, or spontaneous abortion should always be classified as a SAE and

expeditiously reported to the Sponsor. Some examples of pregnancy related SAEs are, but not limited to, the following conditions: placental abruption, placenta previa, pre-eclampsia, prematurity, fetal death, congenital anomaly, or birth defects.

### **10.8.1 Female Subjects Who Become Pregnant**

- The investigator will collect pregnancy information on any female subject who becomes pregnant while participating in this study. Information will be recorded on the appropriate form and submitted to the sponsor within 24 hours of learning of a subject's pregnancy. The participant will be followed to determine the outcome of the pregnancy. The investigator will collect follow-up information on the subject and the neonate, and the information will be forwarded to the sponsor. Generally, follow-up will not be required for longer than 6 to 8 weeks beyond the estimated delivery date. Any termination of pregnancy will be reported, regardless of fetal status (presence or absence of anomalies) or indication for the procedure.
- While pregnancy itself is not considered to be an AE or SAE, any pregnancy complication will be reported as an AE or SAE. A spontaneous abortion or elective termination is always considered to be an SAE and will be reported as such. Any post-study pregnancy-related SAE considered reasonably related to the study intervention by the investigator will be reported to the sponsor as described in Section 10.5.2. While the investigator is not obligated to actively seek this information in former study subjects, he or she may learn of an SAE through spontaneous reporting.

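### Protocol 10.8 and 10.8.1 disagree on whether elective termination of a normal pregnancy is an SAE, so the 24-hour SAE deadline and the TESAE count are unsettled for that event

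*Protocol*

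**What the plan says.** Protocol 10.8 (Exposure to Investigational Product during Pregnancy) exempts certain pregnancy events from SAE status: "Inpatient hospitalization for a normal vaginal delivery or elective abortion of a normal fetus does not constitute a SAE". It then lists the abortions that are serious without exception: "Accidental, therapeutic, or spontaneous abortion should always be classified as a SAE". Elective abortion is not on that list.

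Protocol 10.8.1 (Female Subjects Who Become Pregnant) has its own list, and elective termination is on it: "A spontaneous abortion or elective termination is always considered to be an SAE and will be reported as such". It makes no exception for a normal fetus. The same section requires reporting whatever the SAE status: "Any termination of pregnancy will be reported, regardless of fetal status (presence or absence of anomalies) or indication for the procedure". That sentence carries no deadline. The section's 24-hour clock belongs to the pregnancy form, which is to be "submitted to the sponsor within 24 hours of learning of a subject's pregnancy".

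Protocol 10.5.2 sets the SAE deadline: "Any SAE occurring during the study period (beginning with informed consent) and through 30 days after study exit must be reported within 24 hours". The fetal criterion in the general SAE definition, Protocol 10.5.1, covers an event that "led to fetal distress, fetal death or a congenital abnormality or birth defect". SAP 9.2.2, in the subsection on SAEs and deaths, repeats that criterion. Neither definition names elective termination.

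**The concern.** Sections 10.8 and 10.8.1 sit next to each other and point in opposite directions on one event: elective termination when the fetus is normal. Two things hang on the answer.

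The first is timing. SAE status brings the 24-hour report on the drug and device SAE forms. Without it, the termination must still be reported, but the text gives no deadline for doing so.

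The second is the analysis. SAP 9.2.1 (Treatment-Emergent Adverse Events) makes a TEAE a TESAE when it also meets an SAE criterion, and TESAEs feed the overview table and the tables by system organ class and preferred term. With about 7 sites, two sites could classify the same event differently and each cite the protocol for it.

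**Working it through.** The plan states no figure on this point, so the check sets the texts side by side.

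| Question | Protocol 10.8 | Protocol 10.8.1 |
|---|---|---|
| Which abortions are SAEs in every case? | Accidental, therapeutic, spontaneous | Spontaneous, elective |
| Any exemption when the fetus is normal? | Yes, worded around inpatient hospitalization | None |
| Elective termination, normal fetus | Not an SAE, by the exemption and the omission together | SAE |
| Must an elective termination be reported at all? | Not addressed | Yes, whatever the fetal status or reason |

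1. **Where the sections collide.** The exemption in 10.8 is limited to a normal fetus. For an elective termination with an abnormal fetus, 10.8 states no exemption and 10.8.1 says SAE. The conflict is therefore confined to the normal-fetus case.

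2. **Does the omission from the 10.8 list prove anything alone?** No. A list of events that are always serious does not say that everything else is never serious. Its weight comes from standing beside an exemption for that same event.

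3. **Does the hospitalization wording remove the conflict?** Suppose 10.8 means only that a hospital admission does not by itself make the event serious. Under 10.8.1 the termination would be an SAE anyway, so removing the hospitalization ground would change nothing for it. The exemption would be without effect for elective abortion, and the two lists would still differ on it.

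4. **Does another section decide?** Protocol 10.5.1 and SAP 9.2.2 do not name elective termination. SAP Appendix C, which lists changes to the planned analyses, does not mention it. No rule of precedence between 10.8 and 10.8.1 is given.

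5. **Effect on timing.** For an event between consent and 30 days after study exit:
   - not an SAE: the 10.5.2 deadline does not apply, and the termination is reported under 10.8.1 with no stated deadline;
   - SAE: the 24-hour deadline in 10.5.2 applies.

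   The 24-hour pregnancy clock does not fill the gap, because it starts when the site learns of the pregnancy and not of its termination.

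6. **Effect on the tables.** One event adds one subject, or none, to the TESAE count. If all 60 planned subjects are in the Safety Population, the overall percentage moves by 1/60 = 1.7 percentage points. A smaller Safety Population would give a larger step, as would the columns by treatment group and gender, whose sizes the documents do not give. This shows scale only. It does not predict that such an event will occur.

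**The case against.** The strongest objection is that 10.8 and 10.8.1 address different things. The subject of the 10.8 sentence is inpatient hospitalization, and the sentence after it also concerns pregnancy in the setting of hospitalization. Section 10.8 opens with the duties of marketing authorization holders, while 10.8.1 gives the investigator a direct instruction. A site that follows 10.8.1 reports the event as an SAE and misses no deadline, and the sponsor evaluates all SAEs, so some inconsistencies could be caught centrally.

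Part of this stands. The hospitalization wording makes the clash less flat than two bare opposite statements, and it would be too strong to say that no reading lets a site satisfy both sections. But the narrow reading leaves the exemption idle for this event and the two lists unequal. Central review is also weaker protection where a site relied on 10.8 and submitted no SAE form.

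A reader might infer that the termination could go unreported altogether. The text does not support that, because 10.8.1 requires every termination to be reported.

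The practical weight is small. Women of childbearing potential must use contraception and have a negative test before each injectable treatment, and the event must also fall within the SAE window.

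**Conclusion.** The inconsistency is real and in the current protocol text. It is limited to the SAE status of elective termination with a normal fetus, and through that to the 24-hour SAE deadline and to TESAE counting for events on or after first treatment.

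Its size is at most one subject per event in descriptive tables. The 1.7-point figure rests on the assumption that all 60 planned subjects are treated. It would be tempting to infer a threat to the trial's safety conclusions, but the documents do not support that: no safety hypothesis test is planned, no numerical stopping rule depends on an SAE count, and no efficacy analysis is touched. This is a minor point, worth correcting because it concerns an expedited reporting duty and is cheap to settle.

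**What to change.** Reconcile Protocol 10.8 and 10.8.1 so that both give the same SAE classification for elective termination, and state whether a normal fetus makes a difference. If the hospitalization sentence is kept, say what it is meant to exempt. Apply the agreed classification to the TESAE summaries in the SAP, so that the tables and the site reports follow one rule. A cross-reference from the SAE definition in 10.5.1 would help but is optional. Which classification to adopt is for the sponsor to decide.

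The cost is a short clarification to the two protocol sections and a line in the SAP. No new data, visits or subjects are needed. Even if enrolment is well advanced, settling the rule before database lock would fix how any such event is counted.
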